1.1 Title

Dabigatran versus Warfarin in Patients with Atrial Fibrillation ([RELY](#) trial)

1.2 Intended aim(s)

To compare the risk of stroke or systemic embolism in atrial fibrillation (AF) patients with dabigatran versus warfarin use.

1.3 Primary endpoint for replication

The primary outcome of the study was stroke and systemic embolism.

1.3.1 Required power for primary endpoint and noninferiority margin (if applicable)

Assuming a 2-year recruitment period and at least 1 year of follow-up and a primary event rate of 1.6% per year, it was determined that at least 15,000 patients would be needed to achieve a minimum of 450 events. The study would have approximately 84% power to conclude noninferiority of dabigatran over warfarin at alpha of 0.025 (1-sided) level.

1.4 Secondary endpoint for replication (assay sensitivity) and RCT finding

Major bleeding; RR = 0.93 (95% CI 0.81-1.07)

1.5 Trial estimate

RR = 0.66 (95% CI 0.53-0.82) comparing 150mg dabigatran vs warfarin (Connolly et al., 2009)

2. Person responsible for implementation of replication in Action

[name], MPH and [name] implemented the study design in the Aetion Evidence Platform. They are not responsible for the validity of the design and analytic choices. All implementation steps are recorded and the implementation history is archived in the platform.

3. Data Source(s)

[figure not shown]
United/Optum, MarketScan, Medicare

4. Study Design Diagram

The study design diagram visualizes key aspects of the longitudinal study design for expedited review.

Figure 1.

Design Diagram – RE-LY TRIAL REPLICATION

5. Cohort Identification

5.1 Cohort Summary

This study will involve a new user, parallel group, propensity score-matched, retrospective cohort study design comparing dabigatran (150mg) to warfarin users. The patients will be required to have continuous enrollment during a baseline period of 180 days before initiation of dabigatran or warfarin (index date). We will restrict the analyses to patients with a diagnosis of AF with risk factors for stroke or systemic embolism in the 12 months prior to drug initiation.

5.2 Important steps for cohort formation

New users (defined as no use in 180 days prior to index date) of an exposure and a comparator drug will be identified.

5.2.1 Eligible cohort entry dates

Market availability of dabigatran in the U.S. for non-valvular atrial fibrillation started on October 19, 2010

- For Medicare: October 19, 2010 – December 31, 2017 (end of available data)
- For Marketscan: October 19, 2010 – December 31, 2018 (end of available data)
- For Optum: October 19, 2010 – December 31, 2019 (end of available data)

5.2.2 Specify inclusion/exclusion criteria for cohort entry and define the index date

Inclusion and exclusion criteria were adapted from the trial as closely as possible. Definitions for all inclusion/exclusion are provided in **Appendix A** and are summarized in the flowcharts below.

5.3 Flowchart of the study cohort assembly

For dabigatran 150mg vs. warfarin

	Optum		Truven		Medicare	
	Less Excluded Patients	Remaining Patients	Less Excluded Patients	Remaining Patients	Less Excluded Patients	Remaining Patients
All patients		77,673,639		200,203,908		6,886,908
Did not meet cohort entry criteria	76,847,731	825,908	199,014,982	1,188,926	-2,335,930	4,550,978

Excluded due to insufficient enrollment	-80,642	745,266	-107,905	1,081,021	-1,565,261	2,985,717
Excluded due to prior use of referent	-564,968	180,298	-751,832	329,189	-2,241,426	744,291
Excluded due to prior use of exposure	-44,640	135,658	-71,891	257,298	-196,688	547,603
Excluded because patient qualified in >1 exposure category	-5	135,653	-9	257,289	-24	547,579
Excluded based on Dabigatran (dose other than 150mg)	-306	135,347	-534	256,755	-2,557	545,022
Excluded based on Age	0	135,347	0	256,755	-162	544,860
Excluded based on Gender	0	135,347	0	256,755	0	544,860
Excluded based on Inclusion 1a or 1b or 1 c - Atrial fibrillation	-71,189	64,158	-135,349	121,406	-220,602	324,258
Excluded based on Inclusion 2a-2e History of Stroke, TIA, Systemic embolism / EF<40% / NYHA 2 or higher / Age >75 / Age 65+RF	-11,313	52,845	-17,737	103,669	-24,940	299,318
Excluded based on Inclusion 3 - Age >= 18	-1	52,844	-1	103,668	0	299,318
Excluded based on Exclusion 1 - History of heart valve disorders	-17,688	35,156	-5,687	97,981	-94,948	204,370
Excluded based on Exclusion 2a - Severe/disabling stroke	-576	34,580	-1,111	96,870	-3,090	201,280
Excluded based on Exclusion 2b - Any stroke	-960	33,620	-1,391	95,479	-3,948	197,332
Excluded based on Exclusion 3a - Major Surgery	-1,091	32,529	-2,526	92,953	-6,491	190,841
Excluded based on Exclusion 3c - Intracranial hemorrhage - Inpatient	-51	32,478	-331	92,622	-595	190,246
Excluded based on Exclusion 3d - Gastrointestinal hemorrhage	-4,848	27,630	-1,601	91,021	-5,353	184,893
Excluded based on Exclusion 3e - Symptomatic or endoscopically documented gastroduodenal ulcer disease	-121	27,509	-714	90,307	-3,148	181,745
Excluded based on Exclusion 3f - Hemorrhagic disorder or bleeding diathesis	-257	27,252	-756	89,551	-1,787	179,958
Excluded based on Exclusion 3i - Uncontrolled hypertension	-51	27,201	-400	89,151	-804	179,154

Excluded based on Exclusion 7 - Severe renal impairment	-1,301	25,900	-4,674	84,477	-12,016	167,138
Excluded based on Exclusion 8 & 9 - Active infective endocarditis and liver disease	-36	25,864	-255	84,222	-616	166,522
Excluded based on Exclusion 10 & 11 - Pregnancy & Anemia and Thrombocytopenia	-191	25,673	-1,229	82,993	-2,798	163,724
Excluded based on Exclusion 14 - Alcohol abuse or dependence	-28	25,645	-103	82,890	-138	163,586
Excluded based on Exclusion 14 - Drug abuse or dependence	-22	25,623	-47	82,843	-111	163,475
Excluded based on Exclusion 14 - CCI (180 days)	-7	25,616	-47	82,796	-1,939	161,536
Final cohort		25,616		82,796		161,536

* Medicare database includes all patients using a novel oral anticoagulant and a subset of patients using warfarin during 2011-2017.

6. Variables

6.1 Exposure-related variables:

Study drug:

The study exposure of interest is initiation of dabigatran. Initiation will be defined by no use of dabigatran or a comparator in the prior 6 months before treatment initiation (washout period).

Comparator agents-

- Initiators of dabigatran (150mg) will be compared to initiators of-
 - Warfarin

6.2 Covariates:

- Age
- Sex
- Combined Comorbidity Index (CCI), measured over the baseline covariate assessment period, defined as 180 days prior to and including index date

Covariates listed above represent only a small subset of covariates that will ultimately be controlled for in the design and analysis. We use the covariates above only for initial feasibility analyses to judge whether there is likely to be sufficient overlap between treatment groups to proceed with the study. Remaining covariates are defined only after the study has passed the initial feasibility analysis and the initial power assessment and are listed in Table 1 (**Appendix B**).

6.3 Outcome variables and study follow-up:

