Appendix A

#	RE-LY trial definitions	Implementation in routine care	References/Rationale	Color coding
	Trial details- Primary approval; Unintended 5 with label change		Please see the following Google Drive for further details or any missing information: https://drive.google.com/open?id=1WD618wrywYIeaXrlTcuK-Vcnb6b-g2	Criteria
	EXPOSURE vs. COMPARISON		ICD-10 codes are not listed in this document because of excel cell size limitations and excessive number of ICD-10 codes. Full ICD-10 code lists will be available in the above Google Drive Folder (link above). ICD-9 to ICD-10 code conversions were completed using a SAS macro that implements forward/ backward mapping based on the CMS ICD-9 to ICD-10 mapping: https://www.ncbi.nlm.nih.gov/pmc/articles/PMC2907330/	Adequate mapping in claims
	Fixed doses of dabigatran (110 mg or 150 mg twice daily) vs. adjusted-dose warfarin	Dabigatran (110mg or 150mg twice daily) vs adjusted-dose warfarin		Intermediate mapping in claims
	PRIMARY OUTCOME			Poor mapping or cannot be measured in claims

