Appendix A

1 History of heart valve disorders (ie, prosthetic valve or hemodynamically relevant valve disease)
	
Measured anytime prior to and including day of drug initiation in any diagnosis position and inpatient care setting 394.x (diseases of mitral valve), 395.x (diseases of aortic valve), 396.x (diseases of mitral and aortic valve) 397.x (diseases of other endocardial structures), 398.9x (other and unspecified rheumatic heart diseases) V42.2 (heart valve replaced by transplant), V43.3 (heart valve replaced by a mechanical device/prosthesis) -OR- ICD-9 procedure code 35.1x (open heart valvuloplasty without replacement), 35.2x (replacement of heart valve) -OR- one of the following CPT codes: 33660-33665 (atrioventricular valve repair) 33400-33403 (aortic valve valvuloplasty) 33405 (Replacement, aortic valve, with cardiopulmonary bypass; with prosthetic valve other than homograft or stentless valve) 33420-33430 (mitral valve repair/valvuloplasty/replacement) 33460 (valvectomy, tricuspid valve, with cardiopulmonary bypass) 33463-33468 (tricuspid valve repair/valvuloplasty/replacement) 33475 (replacement, pulmonary valve) 33496 (prosthetic valve dysfunction repair) 025.1 (implantation of catheter-delivered prosthetic aortic heart valve; open thoracic approach) 0258T (transthoracic cardiac exposure for catheter-delivered aortic valve replacement; without cardiopulmonary bypass) 0259T (transthoracic cardiac exposure for catheter-delivered aortic valve replacement; with cardiopulmonary bypass) 0262T (implantation of catheter-delivered prosthetic pulmonary valve, endovascular approach)
	

Severe, disabling stroke within the previous 6 months 2 or Any stroke within the previous 14 days
	
1) Disabling stroke effects Measured 180 days prior to and including day of drug initiation in any diagnosis position and inpatient or outpatient care setting ICD-9 diagnosis: 438.xx (Late effects of cerebrovascular disease) ICD-10 diagnosis: I69 (Sequelae of cerebrovascular disease (hemiplegia etc)) ICD10 diagnosis: Z73.6 (Limitation of activities due to disability) -OR- 2) Any stroke: Measured 14 days prior to and including day of drug initiation in primary diagnosis position and inpatient care setting ICD-9 diagnosis: 430.xx, 431.xx, 433.xx, 434.xx, 436.xx
	

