Appendix A

		Measured 365 days prior to and including day of drug initiation in any diagnosis position and inpatient or outpatient care setting: ICD-9 diagnosis: 578.x Gastrointestinal hemorrhage ICD-10 diagnosis: K92.2: Gastrointestinal hemorrhage, unspecified acute hemorrhagic gastritis (K29.01) peptic ulcer with hemorrhage (K25.x - excluding K25.9 - K26.x - excluding K26.9 - K27.x-K28.x) gastritis and duodenitis with hemorrhage (K29.x) diverticular disease with hemorrhage (K57.x) angiomyolipoma of stomach with hemorrhage (K31.811) CPT/HCPGS: 0W3P8Z - (ICD10) Control Bleeding in Gastrointestinal Tract, Via Natural or Artificial Opening Endoscopic 43255 - (HCPGS) Esophagogastroduodenoscopy, flexible, transoral; with control of bleeding, any method / Upper gastrointestinal endoscopy including esophagus, stomach, and either the duodenum and/or jejunum as appropriate; with control of bleeding, any method 44.43 - (ICD9) ENDOSCOPIC CONTROL OF GASTRIC OR DUODENAL BLEEDING	
	3e • Symptomatic or endoscopically documented gastroduodenal ulcer disease in the previous 30 days	Measured 30 days prior to and including day of drug initiation in any diagnosis position and inpatient or outpatient care setting: ICD-9 diagnosis: Disease of esophagus: 530.1x-530.4x, 530.8x, 530.9x Gastric ulcer: 531.x Duodenal ulcer: 532.x Peptic ulcer: 533.x Acute gastritis: 535.0x Other specified gastritis: 535.4x Unspecified gastritis and gastroduodenitis: 535.5x Duodenitis: 535.6x ICD-10 diagnosis: Peptic ulcer, site unspecified K27.x K25.9 - Gastric ulcer, unspecified as acute or chronic, without hemorrhage or perforation K26.9 Duodenal ulcer, unspecified as acute or chronic, without hemorrhage or perforation	
	3f • Hemorrhagic disorder or bleeding diathesis	Measured 180 days prior to and including day of drug initiation in any diagnosis position and inpatient or outpatient care setting Bleeding diathesis: ICD-9 diagnosis: 286.x Coagulation defects 287.x Purpura and other hemorrhagic conditions ICD-10 diagnosis: D65.x Disseminated intravascular coagulation [defibrination syndrome] D66.x Hereditary factor VIII deficiency D67.x Hereditary factor IX deficiency D68.x Other coagulation defects D69.x Purpura and other hemorrhagic conditions	
3g	• Need for anticoagulant treatment of disorders other than Atrial fibrillation	N/A	

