...mean (sd)	0.08 (0.35)	0.09 (0.36)	-0.03	0.07 (0.40)	0.08 (0.35)	-0.03	0.11 (0.41)	0.13 (0.42)	-0.05	0.10 (0.40)	0.11 (0.39)	-0.03
...median [IQR]	0.00 [0.00, 0.00]	0.00 [0.00, 0.00]	0.00	0.00 [0.00, 0.00]	0.00 [0.00, 0.00]	0.00	0.00 [0.00, 0.00]	0.00 [0.00, 0.00]	0.00	0.00 (0.46)	0.00 (0.43)	0.00
Number of Cardiac biomarkers tests (tropnin, CK-MBs, Myoglobin, CPK)												
...mean (sd)	0.22 (0.91)	0.37 (1.23)	-0.14	0.21 (0.98)	0.32 (1.30)	-0.10	0.19 (0.49)	0.25 (0.56)	-0.11	0.20 (0.72)	0.28 (0.93)	0.00
...median [IQR]	0.00 [0.00, 0.00]	0.00 [0.00, 0.00]	0.00	0.00 [0.00, 0.00]	0.00 [0.00, 0.00]	0.00	0.00 [0.00, 0.00]	0.00 [0.00, 0.00]	0.00	0.00 (0.90)	0.00 (1.13)	0.00
Number of Ambulatory Blood pressure monitoring tests												
...mean (sd)	0.00 (0.03)	0.00 (0.03)	0.00	0.00 (0.04)	0.00 (0.04)	0.00	0.00 (0.02)	0.00 (0.04)	0.00	0.00 (0.03)	0.00 (0.04)	0.00
...median [IQR]	0.00 [0.00, 0.00]	0.00 [0.00, 0.00]	0.00	0.00 [0.00, 0.00]	0.00 [0.00, 0.00]	0.00	0.00 [0.00, 0.00]	0.00 [0.00, 0.00]	0.00	0.00 (0.04)	0.00 (0.04)	0.00
N of days on antihypertensive medications during baseline												
...mean (sd)	130.02 (68.95)	129.85 (66.94)	0.00	135.76 (65.79)	131.96 (67.63)	0.06	138.23 (64.13)	137.11 (64.13)	0.02	136.67 (65.13)	134.83 (65.56)	0.00
...median [IQR]	171.00 [89.00, 181.00]	168.00 [91.00, 181.00]	0.04	174.00 [110.00, 181.00]	171.00 [94.00, 181.00]	0.04	174.00 [122.00, 181.00]	173.00 [116.00, 181.00]	0.02	121.24 (74.47)	130.61 (73.42)	0.00
N of days in database anytime prior												
...mean (sd)	1,750.74 (1,238.00)	1,753.82 (1,191.57)	0.00	2,172.37 (1,246.30)	2,083.21 (1,203.95)	0.07	833.53 (537.51)	873.46 (457.48)	-0.08	1325.93 (889.77)	1352.52 (849.34)	0.00

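### Valve and GI-hemorrhage exclusion yields differ several-fold between databases with no explanation, the stated nursing-home exclusion is undocumented, and the Optum hospitalization covariates do not work

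*Combined protocol and SAP*

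**What the plan says.** Section 5.2.2: "Definitions for all inclusion/exclusion are provided in" Appendix A, and the flowcharts in Section 5.3 summarize them. Appendix A has one entry per criterion, with no variant by database.

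- **Exclusion 1 (valve disease):** the flowchart row is "Excluded based on Exclusion 1 - History of heart valve disorders". Its Appendix A definition is "Measured anytime prior to and including day of drug initiation in any diagnosis position and inpatient care setting". Exclusion 3c (intracranial and other bleeding) carries the same timing, position and setting.
- **Exclusion 3d (GI hemorrhage):** 365-day look-back, any diagnosis position, inpatient or outpatient, starting from "ICD-9 diagnosis: 578.x Gastrointestinal hemorrhage ICD-10 diagnosis: K92.2: Gastrointestinal hemorrhage, unspecified" and adding several ICD-10 families.
- **Code lists:** Appendix A states "Full ICD-10 code lists will be available in the above Google Drive Folder (link above"). The visible entry for Exclusion 1 lists ICD-9 and CPT codes only.
- **Entry windows (Section 5.2.1):** all open on 19 October 2010 and close at the end of 2017 (Medicare), 2018 (MarketScan) and 2019 (Optum).
- **Nursing home (Section 6.3.2):** admission is a censoring event and, for the same reason, is also to be a cohort exclusion.

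**The concern.** If one rule was run on three claims databases, yields should differ by case mix and coding habits. A sixfold spread on valve disease and an eightfold excess of GI hemorrhage in one database are larger than that usually produces. They are also larger than nearly every other exclusion step in this flowchart shows. A reader cannot tell whether the three cohorts were selected by the same rules, or whether each matches the trial criteria that the study sets out to emulate. At stake are fidelity to those criteria and comparability of the databases before pooling.

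The nursing-home exclusion matters because Section 6.3.2 itself says that drug use is poorly recorded after admission. The Optum covariates matter because Section 9 relies on a propensity score with the full covariate list.

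**Working it through.** **1. The flowchart's own arithmetic.** Previous remaining minus excluded, over 26 rows and three databases, reproduces every count, ending at 25,616 / 82,796 / 161,536 (Optum / MarketScan, headed Truven / Medicare). For example, 52,844 − 17,688 = 35,156. The contrast is not a subtraction error.

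**2. Step yields** (excluded ÷ remaining at the previous row):

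| Step | Optum | MarketScan | Medicare |
|---|---|---|---|
| 1 Valve | 17,688/52,844 = 33.5% | 5,687/103,668 = 5.5% | 94,948/299,318 = 31.7% |
| 3d GI hemorrhage | 4,848/32,478 = 14.9% | 1,601/92,622 = 1.7% | 5,353/190,246 = 2.8% |
| 3c Intracranial hemorrhage | 51/32,529 = 0.16% | 331/92,953 = 0.36% | 595/190,841 = 0.31% |
| 2b Any stroke, 14 days | 960/34,580 = 2.8% | 1,391/96,870 = 1.4% | 3,948/201,280 = 2.0% |

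Optum to MarketScan is 6.1-fold for valve disease and 8.6-fold for GI hemorrhage; Medicare to MarketScan is 5.8-fold for valve disease. Apart from valve, GI hemorrhage and the comorbidity-index step, the other twelve exclusion rows spread 1.2- to 3.9-fold. Chance is not a candidate (chi-square about 29,300 and 12,800 on 2 df).

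For scale at the valve step only: MarketScan's yield would exclude about 2,899 in Optum and 16,420 in Medicare. Conversely, the Medicare or Optum yield would exclude about 32,900 or 34,700 in MarketScan.

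**3. Possible innocent explanations.**

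- *Look-back.* The Appendix B row "N of days in database anytime prior" gives unmatched warfarin means of 1,751 / 2,172 / 834 days. MarketScan has the longest history and the lowest yield on an any-time-prior rule. These means describe retained patients only.
- *Inpatient capture.* Exclusion 3c has the same setting and look-back as Exclusion 1, and MarketScan is not low there.
- *Medicare's warfarin subset* (flowchart footnote) cannot affect the Optum–MarketScan contrast.
- *Optum's extra year.* Assume even entry over its 3,361-day window: 2019 then holds 365/3,361 = 10.9% of entrants. If all of them were excluded and the rest followed MarketScan, yields would be 0.109 + 0.891 × 0.0549 = 15.7% (valve) and 0.109 + 0.891 × 0.0173 = 12.4% (GI). To reach the observed yields, the 2019 share would have to be (0.3347 − 0.0549)/0.9451 = 29.6% (valve) or (0.1493 − 0.0173)/0.9827 = 13.4% (GI). This is an illustration, not a bound: the calendar mix within shared years is not reported.

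**4. Nursing home.** Section 6.3.2 states the exclusion. Section 5.3 has no row for it, and the Appendix A criteria have no entry, code list or look-back. Section 9 shows admission only in a censoring row combined with switching to other anticoagulants (6,073 patients, 7.77%).

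**5. Optum hospitalization** (Appendix B, unmatched). Any hospitalization: 0 of 22,665 + 2,936 = 25,601. MarketScan has 17,074 + 4,804 = 21,878 of 82,719 (26.4%); Medicare has 19,589 + 4,815 = 24,404 of 161,317 (15.1%). Yet Optum warfarin hospital days have SD 0.11, so at least one patient has hospital days without a hospitalization. Inpatient-only steps 2b and 3c removed 960 and 51 Optum patients, so inpatient records exist there. Standardized differences before matching are −0.16 (MarketScan) and −0.13 (Medicare).

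**The case against.** The full ICD-10 lists sit outside the document, so whether the same codes ran everywhere cannot be judged from it. Optum's later entry, together with broad ICD-10 families for GI hemorrhage, could account for part of that excess. The Medicare–MarketScan GI contrast (1.6-fold) is within the ordinary spread, so only Optum stands out on 3d. Database time among retained patients is conditioned on the step being examined: an any-time-prior exclusion tends to remove people with long histories. This weakens the Optum comparison, but it does not readily explain Medicare's high yield alongside 834 days. The design diagram is not available in the text and may mention nursing homes, and post-admission time is censored anyway. All of this stands. It leaves the valve contrast without a stated reason and the nursing-home exclusion without a definition or count.

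A reader might go further in three ways that the documents do not support.

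- *That an exclusion failed, or that MarketScan is the database in error.* Nothing shows the cause or the correct yield.
- *That expected events and power would shift in proportion to cohort size.* Section 10 counts matched pairs, which use 39,070/43,095 = 90.7% of dabigatran but only 39,070/226,542 = 17.2% of warfarin initiators. Without yields by arm, whole-cohort changes cannot be carried over to matched events.
- *That residual counts under exclusion-like covariate names in Appendix B, such as malignant hypertension, prove leakage.* Those rows do not follow Appendix A definitions: atrial fibrillation, required of everyone, is flagged in only 94.6% / 91.5% / 88.6%.

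**Conclusion.** The point holds as a gap in consistency and documentation, with one working defect in a covariate. Valve yields of 33.5 / 5.5 / 31.7% and an Optum GI yield of 14.9% against 1.7% and 2.8% are hard to reconcile with one definition each, and no reason is given. The nursing-home exclusion is either unapplied or undocumented. The Optum hospitalization covariates are internally inconsistent and cannot adjust for hospitalization in that database, which supplies 5,580/78,140 = 7.1% of matched patients.

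The counts are certain; the cause is not identified. No bias in any hazard ratio is shown, and the effect on matched size and power cannot be computed from the documents. The small loss between the final flowchart counts and Appendix B (15 / 77 / 219 patients) and the low comorbidity-index yields are minor queries that do not bear on this conclusion.

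**What to change.** Before Section 13 is run:

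1. For Exclusions 1 and 3d, compare the implemented ICD-9 and ICD-10 codes, care setting and look-back in each database with Appendix A and its external lists. Where a database departs, correct it, rematch and reissue Sections 5.3, 9 and 10. Where none departs, state the reason for the difference, for example with yields by calendar year or code era. Report these yields by treatment arm as well.
2. Confirm whether the nursing-home exclusion was run, and apply it if not. Either way, define it in Appendix A with its look-back and show its count as a flowchart row.
3. Correct the Optum hospitalization covariates, refit the Optum propensity score and rematch.

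The cost is programming and reruns on data already held. Matched sizes and stated power may change. If item 1 finds no departure, it costs only a short explanation; if the nursing-home exclusion was already run, item 2 costs one definition and one row.

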6.3.2 Study follow-up

Both as-treated (AT) and intention-to-treat (ITT) analyses will be conducted with treatment defined as the index drug on the day of cohort entry. Because adherence in the real-world databases is expected to be much worse than in the trial, the AT analysis is the **primary** analysis, as it targets the relative hazard of outcomes on treatment.

For the AT analyses, the follow-up will start the day after initiation of apixaban and comparator and will continue until the earliest date of the following events:

- The first occurrence of the outcome of interest, unless otherwise specified for selected outcomes,
- The date of end of continuous registration in the database,
- End of the study period,
- Measured death event occurs,

- Nursing home admission
 - Nursing home admissions are considered a censoring event because the data sources utilized typically provide little to no data on a patient, particularly on drug utilization, after admission. We will utilize this as an exclusion reason for cohorts for the same reason.
- The date of drug discontinuation, defined as the date of the last continuous treatment episode of the index drug (dabigatran and comparator) plus a defined grace period (i.e., 10 days after the end of the last prescription's days' supply in main analyses).
- The date of augmentation or switching from exposure to comparator or vice versa or augmentation/switching to any other NOAC (e.g. switching from dabigatran or warfarin to apixaban would be a censoring event);
 - A dosage change on the index treatment does not fulfill this criterion
 - An added treatment that is not part of the exposure or comparator group does not fulfill this criterion
- Dispensing of a fibrinolytic agent

For the intention-to-treat (ITT) analyses, the censoring based on the augmentation/switching and treatment discontinuation will be replaced with a maximum allowed follow-up time of 365 days.

7. Initial Feasibility Analysis

Action report name:

For dabigatran vs. warfarin

Optum- <https://bwh-dope.aetion.com/projects/details/707/results/59579/result/0>

Marketscan- <https://bwh-dope.aetion.com/projects/details/708/results/59601/result/0>

Medicare- <https://bwh-dope.aetion.com/projects/details/709/results/59602/result/0>

Date conducted: 10/5/20 (Medicare 10/6/20)

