After review of initial feasibility and power analyses, complete creation of the remaining covariates (see Table 1 below for list of covariates). Again, using the dummy outcome of a 90-day gap in database enrollment, complete a 1:1 PS-matched analysis. The PS should include the complete list of covariates (excluding laboratory values, which are missing in some patients).

- Provide plot of PS distributions stratified by treatment group.

Note- Please refer to **Appendix B**.

- Report covariate balance after matching.

Note- For Table 1, please refer to **Appendix B**.

- Report reasons for censoring by treatment group.

	Overall	Referent	Exposure
Dummy Outcome	0 (0.00%)	0 (0.00%)	0 (0.00%)
Death	657 (0.84%)	369 (0.94%)	288 (0.74%)
Start of an additional exposure	2,760 (3.53%)	1,189 (3.04%)	1,571 (4.02%)
End of index exposure	62,039 (79.39%)	31,190 (79.83%)	30,849 (78.96%)
Specified date reached (Dec 17/Dec 18/Dec 19)	2,483 (3.18%)	1,281 (3.28%)	1,202 (3.08%)
End of patient enrollment	4,128 (5.28%)	1,938 (4.96%)	2,190 (5.61%)
Switch to other NOACs (for censoring) + nursing home admission	6,073 (7.77%)	3,103 (7.94%)	2,970 (7.60%)

- Report follow-up time by treatment group.

Median Follow-Up Time (Days) [IQR]			
Patient Group	Optum	Truven	Medicare
Overall Patient Population	98 [38-191]	98 [38-193]	98 [38-202]

Referent	98 [43-192]	98 [43-178]	98 [42-196]
Exposure	98 [38-190]	98 [38-220]	98 [38-211]

- Report overall risk of the primary outcome.

	Optum	MarketScan	Medicare	Pooled
Risk per 1,000 patients	4.57	5.20	6.04	5.64

10. Final Power Assessment

Date conducted:

- Re-calculate power in the appropriate excel table, using the revised number of matched patients from the PS-match in Section 9. All other parameters in the table should be the same as in Section 8. If the study is to be implemented in more than one database, copy and paste excel sheet to report power for each database separately and for the pooled analysis that uses data from all databases together. Power calculations are based on the formulas from Chow et al. (2008).
 - For dabigatran 150mg vs. warfarin
 - Pooled

Superiority Analysis		Non-inferiority Analysis	
Number of patients matched	78,140	Number of patients matched	78,140
Reference	39,070	Reference	39,070
Exposed	39,070	Exposed	39,070
Risk per 1,000 patients	5.64	Risk per 1,000 patients	5.64
Desired HR from RCT	0.66	Assumed HR from RCT	1
Alpha (2-sided)	0.05	Alpha (2-sided)	0.05
		Non-inferiority margin	1.46

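### The Medicare referent arm may be selected on later NOAC use, because the extract holds all NOAC users but only a subset of warfarin users, and the plan neither describes nor corrects for this sampling

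*Combined protocol and SAP*

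**What the plan says.** The flowchart footnote in section 5.3 describes the extract: "Medicare database includes all patients using a novel oral anticoagulant and a subset of patients using warfarin during 2011-2017". It does not say how the subset was drawn, what fraction it represents, or whether sampled warfarin users can be told apart from people present because of NOAC use. Its calendar span also differs slightly from the entry window in section 5.2.1: "For Medicare: October 19, 2010 – December 31, 2017 (end of available data".

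Four other parts of the plan bear on this:

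- **Entry (section 6.1).** "Initiation will be defined by no use of dabigatran or a comparator in the prior 6 months before treatment initiation (washout period"). The washout looks backwards only, so NOAC use after the index date does not bar a warfarin initiator from the referent arm.
- **Follow-up (section 6.3.2).** In the primary as-treated (AT) analysis, "switching from dabigatran or warfarin to apixaban would be a censoring event". In the intention-to-treat (ITT) analysis, the censoring for switching and discontinuation "will be replaced with a maximum allowed follow-up time of 365 days".
- **Adjustment (section 9).** The instruction is to "complete a 1:1 PS-matched analysis". No sampling weight appears anywhere in the document.
- **Pooling (section 10).** Power is reported for each database and for "the pooled analysis that uses data from all databases together". Section 13.2, for sensitivity analyses, is empty.

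**The concern.** If NOAC users are taken in full and warfarin users in part, the chance that a Medicare warfarin initiator is in the data depends on what that patient takes after the index date. Dabigatran initiators are not affected, since all of them are included. The selection would therefore act on one arm only.

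Two opposing effects are plausible. A patient must be alive and under care to start a NOAC later, so over-sampling later starters could lower the referent event rate. A stroke on warfarin may itself prompt a switch, which could raise it. The propensity score uses baseline covariates and cannot correct either effect.

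The purpose of the study is to see whether claims data reproduce a trial estimate of 0.66. A sampling artefact in the largest database would make agreement or disagreement with that estimate harder to interpret.

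**Working it through.** **1. The plan's power figures (section 10).** Events = matched patients × risk per 1,000 / 1,000. Power = Φ(√(events/4) × |ln HR| − 1.96), using HR 0.66 for superiority and 1.46 for non-inferiority.

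| | Events | Power, superiority (plan) | Power, non-inferiority (plan) |
|---|---|---|---|
| Pooled | 78,140 × 5.64/1,000 = 440.7 | 0.992 (0.992) | 0.978 (0.978) |
| Medicare | 44,640 × 6.04/1,000 = 269.6 | 0.927 (0.927) | 0.874 (0.874) |

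The plan's figures reproduce. They are not in question.

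**2. Weight of Medicare.** Pairs: 22,320/39,070 = 57.1%. Expected events: 269.6/440.7 = 61.2%.

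**3. Mechanism.** Let p be the true share of warfarin initiators who later use a NOAC, and f the fraction of warfarin-only users sampled. Neither is given. The share of later NOAC users in the extract is q = p/(p + (1 − p)f). Assumed examples:

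- p = 0.20, f = 0.50: q = 0.20/0.60 = 0.33
- p = 0.40, f = 0.25: q = 0.40/0.55 = 0.73
- f = 1: q = p, so no distortion

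**4. Illustrative effect on the hazard ratio.** Let r be the event rate in later NOAC users relative to never users (assumed 0.7 or 1.3). The referent rate is multiplied by k = (qr + 1 − q)/(pr + 1 − p), and the Medicare HR reads 0.66/k. Pooling is on the log scale with Medicare weight 0.612 and 0.66 in the other two databases.

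| p, f | r | k | Medicare HR | Pooled HR |
|---|---|---|---|---|
| 0.40, 0.25 | 0.7 | 0.888 | 0.74 | 0.71 |
| 0.40, 0.25 | 1.3 | 1.088 | 0.61 | 0.63 |
| 0.20, 0.50 | 0.7 | 0.957 | 0.69 | 0.68 |
| 0.20, 0.50 | 1.3 | 1.038 | 0.64 | 0.64 |

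**5. What the documents show about thinning.** Unmatched warfarin:dabigatran ratios (Appendix B):

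- Medicare: 136,087/25,230 = 5.39
- Optum: 22,665/2,936 = 7.72
- MarketScan: 67,790/14,929 = 4.54

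Taken crudely, the share of warfarin initiators kept in Medicare is 5.39/7.72 = 0.70 against Optum and 5.39/4.54 = 1.19 against MarketScan, that is, no thinning. The share kept equals p + (1 − p)f. If the Optum benchmark held and p were 0.20, f would be (0.70 − 0.20)/0.80 ≈ 0.62, and the formulas in step 4 give a pooled HR of 0.65 to 0.67. The populations differ in payer, age and end date, so none of these values is an estimate of f.

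**6. Follow-up and switching (section 9).** Median referent AT follow-up is 98 [42-196] days in Medicare, 98 [43-192] in Optum and 98 [43-178] in MarketScan, so no shortening is visible. Pooled AT censoring for an added exposure, another NOAC or nursing home admission is (1,189 + 3,103)/39,070 = 11.0% in referents and (1,571 + 2,970)/39,070 = 11.6% in the exposed. These counts are not split by database, and they miss NOAC starts after warfarin has stopped. That matters because 79.83% of referents were censored at the end of index exposure.

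**7. Pooled estimate without Medicare.** Patients: 5,580 + 27,920 = 33,500. Events: 25.5 + 145.2 = 170.7. Power: 0.775 for superiority and 0.696 for non-inferiority.

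**The case against.** The strongest reply is that the footnote describes a possibility. Over-sampling needs three things: a subset that is materially incomplete among eligible initiators, drawn without regard to NOAC use, in an extract that carries NOAC users' earlier warfarin history. The documents establish none of these for Medicare. Medicare is not visibly short of warfarin users. The heavier assumptions in step 4 (p = 0.40, f = 0.25) keep only 55% of warfarin initiators, so the unthinned ratio would be 5.39/0.55 = 9.8, above either comparison database. The primary AT analysis censors at a switch. Even the extreme pooled values, 0.63 and 0.71, lie inside the trial interval of 0.53 to 0.82, and power for superiority at 0.71 with 440.7 events is still about 0.95.

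Most of this stands, and it limits the point to a conditional one. It does not remove it. The ratio comparison gives two incompatible answers, so it cannot show that the subset is near-complete. AT censoring happens after a patient has entered the extract, so it does not undo selection into it. The 1,189 matched referents censored for an additional exposure show that patients who start dabigatran after warfarin are in the pooled referent arm, although the table does not say in which database.

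A reader might go further and take the flowchart row "Did not meet cohort entry criteria" as proof. In Medicare it removes 2,335,930 of 6,886,908 people (33.9%), against 98.9% in Optum and 99.4% in MarketScan. That fits an extract chosen by drug use. The row gives no reasons for failure and says nothing about how warfarin users were drawn, so it does not confirm over-sampling.

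**Conclusion.** The point holds in conditional form. If the warfarin subset is materially incomplete and was drawn without removing the dependence on NOAC use, the Medicare referent arm over-represents later NOAC starters, and the planned matching cannot correct this. The arm concerned belongs to a database with 57% of the pairs and 61% of the expected events, and no planned analysis would reveal the problem.

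The size and direction are undetermined. The pooled range of 0.63 to 0.71 around 0.66 rests wholly on assumed p, f and r, and the effect vanishes as f approaches 1. A reader might infer that the arm is known to be over-sampled, or that the hazard ratio is biased by a known amount; the documents support neither.

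The ITT analysis is likely more exposed than AT, because it follows patients through the switch for up to 365 days, so an excess of switchers also changes the treatment received during follow-up. Optum and MarketScan are not covered by the footnote. This is a cheap improvement, not a demonstrated flaw in the estimate.

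**What to change.** Before the comparative analyses in section 13, which carry no date:

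1. State beside the section 5.3 footnote how the Medicare warfarin subset was drawn, its fraction, and whether it can be identified in the extract.
2. Pre-specify in section 13.2 a pooled AT and ITT estimate without Medicare, with its expected 171 events and power of about 0.77 (superiority) and 0.70 (non-inferiority). This needs no information beyond what the study already holds.
3. If the sampled users can be identified, or the fraction is known and below 1, restrict Medicare referents to the sampled subset whatever they used later, or weight referents with no NOAC use by the inverse of the sampling fraction. Then re-match and carry any weights into the outcome model.

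The cost of item 2 is a small amount of extra analysis and a less precise sensitivity estimate. The cost of item 3 cannot be given, because the documents mention no sample indicator or fraction. A smaller referent pool could also lose matches: at 5.39 warfarin users per dabigatran user, 25,230 − 22,320 = 2,910 Medicare dabigatran patients (11.5%) are already unmatched.
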